### **5.2.3 Nivolumab Therapy**

Nivolumab will initially be administered every 3 weeks at a dose of 3 mg/kg for four doses in combination with ipilimumab, and then will be administered at a flat dose of 480 mg every four weeks until study therapy discontinuation.

Dosing window: There is an administration window of -2/+5 days for Nivolumab administrations.

Labs/assessments window: Labs/assessments may be performed up to 7 days prior to Nivolumab doses.

Counting of days will not be continuous on study. In the event of a treatment delay due to a toxicity, the current cycle will be extended until the criteria to resume treatment are met. The day of treatment restart will be the participant's subsequent cycle's Day 1.

If treatment with study medication is delayed > 12 weeks, the participant must be permanently discontinued from study therapy, except as specified in Section 6.4.

Treatment will be administered on an outpatient basis. Reported adverse events and potential risks are described in Section 7. Appropriate dose modifications are described in Section 6. No investigational or commercial agents or therapies other than those described below may be administered with the intent to treat the participant's malignancy.

For details regarding drug storage, preparation, administration, and use time please refer to Section 8 of the protocol and the current BMS-936558 (nivolumab) Investigator Brochure.

Nivolumab is to be administered as an IV infusion over 30 minutes (window of -10 / + 30 min). At the end of the infusion, flush the line with a sufficient quantity of normal saline. On treatment days when both nivolumab and ipilimumab are administered, nivolumab will be administered first with a 30 minute observation window before starting ipilimumab.

### **5.2.4 Ipilimumab Therapy**

Ipilimumab will be administered every 3 weeks at a dose of 1 mg/kg for 4 consecutive doses, with nivolumab.

CONFIDENTIAL

This document is confidential. Do not disclose or use except as authorized.

Dosing window: There is an administration window of -2/+5 days for Ipilimumab administrations; however, participants may be dosed no less than 24 days (23 non-dosing days) between doses.

Labs/assessments window: Labs/assessments may be performed up to 7 days prior to Ipilimumab doses.

Counting of days will not be continuous on study. In the event of a treatment delay due to a toxicity, the current cycle will be extended until the criteria to resume treatment are met. The day of treatment restart will be the participant's subsequent cycle's Day 1.

If treatment with study medication is delayed > 12 weeks, the participant must be permanently discontinued from study therapy, except as specified in Section 6.4.

Treatment will be administered on an outpatient basis. Reported adverse events and potential risks are described in Section 7. Appropriate dose modifications are described in Section 6. No investigational or commercial agents or therapies other than those described below may be administered with the intent to treat the participant's malignancy.

For details regarding drug storage, preparation, administration, and use time please refer to Section 8 of the protocol and the current BMS-734016 (Ipilimumab) Investigator Brochure.

Ipilimumab is to be administered as an IV infusion over 30 minutes (window of -10 / + 30 min). At the end of the infusion, flush the line with a sufficient quantity of normal saline.

On treatment days when both nivolumab and ipilimumab are administered, nivolumab will be administered first with a 30-minute observation window before starting ipilimumab.

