**Dosing window:**

Participants may be dosed no more than 5 days after - and no more than 2 days before - the scheduled dosing date. Dose given after the 5-day window is considered a dose delay.

Cohort 1: Participants may be dosed no less than 12 days (11 non-dosing days) between doses.

Cohort 2: The following minimum intervals are required between nivolumab doses: a minimum 14-day interval (13 non-dosing days) during combination therapy cycles (nivolumab every 3 weeks), and a minimum 21-day interval (20 non-dosing days) during nivolumab monotherapy therapy cycles (nivolumab every 4 weeks).

A maximum delay of 42 days *between doses* is allowed.

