Baseline evaluations are to be conducted within 14 days of start of protocol therapy unless indicated otherwise. Pre-treatment baseline brain MRI must be done  $\leq$  14 days prior to the start of therapy. Cycles are 21-days during Combination Therapy and 28-days during Nivolumab Monotherapy. Study assessments may be performed up to 3 days prior to dosing and must be performed and reviewed prior to administration of any study agent at any treatment visit. Nivolumab and ipilimumab should be administered within -2/+5 days of the protocol-specified date.

Assessments	Screen -ing a	RT	Combination Therapy (Nivolumab + Ipilimumab)		Maintenance Monotherapy (Nivolumab)	D1 b Subsequent Tx Cycles	End of Tx Visit d	30-Day Post Drug e	Active Follow-Up Visit f	Long Term Follow-Up g
			Prior to Cycle 1 D1 b	Cycle 1 D1 b						
Informed consent h	X									
Background information/history i	X									
Inclusion/exclusion criteria j	X									
Vital signs and Oxygen Saturation k	X		X	X	X	X	X			
Full Physical Exam l	X		X	X	X	X	X			
Neurologic Exam m	X		X	X	X	X	X			
Physical Measurements (including KPS) o	X		X	X	X	X	X	X hh		
Concomitant medications p	X				X p					
Adverse event assessment & Recording q					X q					
Recording/Reporting of Serious Adverse Events q						X q				
Pregnancy Test – Urine or Serum $\beta$ -HCG r	X		X							
12-lead ECG s	X									
Hematology t and Serum Chemistry u	X		X	X	X	X	X			
Urinalysis v	X									
FT3, FT4 & TSH w	X		X	X	X	X	X			
Imaging – MRI (or CT) x and NANO Scale z	X			X	X	X	X		X	
Response Assessment y				X	X	X	X		X	
Nivolumab Administration ii			X	X	X					
Ipilimumab Administration jj			X	X						
Radiation Therapy kk		X								
Submission of archival tumor tissue dd			X							
Submission of tumor sample at the time of progression or suspected progression ee							X			
Post-end-of-treatment oncology therapies ff									X	X
Survival gg									X	X

CONFIDENTIAL

This document is confidential. Do not disclose or use except as authorized.

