- hh. KPS only required at 30-Day Post-Drug time point.

CONFIDENTIAL

This document is confidential. Do not disclose or use except as authorized.

- ii. There is an administration window for nivolumab of -2/+5 days
  - There must be a minimum of 14-days (13 non-dosing days) during combination therapy cycles (nivolumab every 3 weeks), and a minimum 21-day interval (20 non-dosing days) during nivolumab monotherapy therapy cycles (nivolumab every 4 weeks)
  - The start and stop time of the nivolumab infusion administration should be documented.
- jj. There is an administration window for ipilimumab of -2/+5 days
  - The start and stop time of the ipilimumab infusion administration should be documented.
  - There must be a minimum of 24 days (23 non-dosing days) between administrations
  - On treatment days when both nivolumab and ipilimumab are administered, nivolumab will be administered first with a 30 minute observation window before starting ipilimumab.
- kk. On-study Radiation Therapy will be administered according to established, institutional standard-of-care guidelines for reirradiation and best clinician judgment. See section 5.2.3 for techniques and locations. On-study RT to occur prior to initiation of Cycle 1 of Nivolumab + Ipilimumab. Day 1 Cycle 1 of study immunotherapy will be no sooner than 1 week from the completion of XRT, and no later than 12 weeks after completion of XRT.

CONFIDENTIAL

This document is confidential. Do not disclose or use except as authorized.

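### The 24-day minimum between ipilimumab doses rules out on-time dosing every 3 weeks in Cohort 2, and the Cohort 2 delay limits disagree (12 weeks against 6)

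*Combined protocol and SAP*

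**What the plan says.** **Ipilimumab interval.** Section 5.2.4: "Ipilimumab will be administered every 3 weeks at a dose of 1 mg/kg for 4 consecutive doses". Table 5.2 and Dose Level 0 in Section 5.2.1 give the same interval, and Section 5.2.1 has ipilimumab given on the same day as nivolumab. The Cohort 2 calendar (Section 10.2) agrees: "Cycles are 21-days during Combination Therapy and 28-days during Nivolumab Monotherapy". It also sets the window: "Nivolumab and ipilimumab should be administered within -2/+5 days of the protocol-specified date".

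**Minimum gap.** For ipilimumab, Section 5.2.4 says "participants may be dosed no less than 24 days (23 non-dosing days) between doses", and calendar footnote jj says "There must be a minimum of 24 days (23 non-dosing days) between administrations". For nivolumab in the same cycles, the dosing-window text in Section 6 sets "a minimum 14-day interval (13 non-dosing days) during combination therapy cycles (nivolumab every 3 weeks").

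**Resetting of dates.** Section 5.2.4 also says "Counting of days will not be continuous on study", although the detail that follows deals with delays for toxicity.

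**Delay limits in Cohort 2.** Sections 5.2.3 and 5.2.4 end study therapy after a delay of more than 12 weeks, subject to Section 6.4. Section 6 allows at most 42 days, counted between doses. Section 6.3 ends study therapy after a delay of more than 6 weeks, with no restriction by cohort. Section 6.4 ends the combination after an interruption of more than 6 weeks counted from the last dose. It excepts prolonged steroid tapers and, with the Overall PI's approval, holds that are not drug-related.

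**The concern.** A minimum gap longer than the planned interval contradicts the schedule it governs. These are operative instructions, and the second copy is in the calendar that sites work from. A site that doses on the scheduled day breaks the minimum. A site that obeys the minimum gives ipilimumab, and with it nivolumab, every 24 to 26 days. That is not the every-3-week regimen that Dose Level 0 is meant to test.

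The delay limits raise a different problem: two sites could reach opposite decisions on the same hold. During combination therapy the remaining ipilimumab doses are at stake, because Section 6.4 allows nivolumab alone after recovery. That allowance covers only events that occur during combination therapy, so in maintenance nivolumab itself is at stake.

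**Working it through.** Gaps are counted in days after the previous dose, or after dose 1 where stated. The study day is one more than the days after dose 1.

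**Part 1: the minimum gap**

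Inputs: interval 21 days, window -2/+5 and ipilimumab minimum 24 (Section 5.2.4, footnote jj); minima of 12 days in Cohort 1, and 14 and 21 days for Cohort 2 nivolumab (Section 6); DLT period of 42 days (Section 5.2.2).

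1. *Can the 24 be reproduced?* The protocol's other minima follow two patterns.
   - Interval minus 2: 14 - 2 = 12, as in Cohort 1. For ipilimumab this gives 21 - 2 = 19.
   - Interval minus 5 minus 2, the shortest gap between two in-window doses on a fixed calendar: 21 - 5 - 2 = 14 and 28 - 5 - 2 = 21, as for Cohort 2 nivolumab. For ipilimumab this gives 14.
   - Neither pattern gives 24.
2. *Dates reset at each dose.* The window is 21 - 2 = 19 to 21 + 5 = 26, which is 8 days. Days 19 to 23 (5 of 8, including day 21) are barred, and days 24 to 26 remain. Dose 4 falls 3 × 24 = 72 to 3 × 26 = 78 days after dose 1, against 3 × 21 = 63 as planned.
3. *Calendar fixed from dose 1.*

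| Dose | Window, days after dose 1 | Earliest under the 24-day rule | In window? |
|---|---|---|---|
| 2 | 19–26 | 24 | yes |
| 3 | 40–47 | 2 × 24 = 48 | no, 1 day late |
| 4 | 61–68 | 3 × 24 = 72 | no, 4 days late |

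4. *Pairs of consecutive in-window doses, fixed calendar.* The gap is 21 + b - a, with a and b each from -2 to +5 (64 pairs). A 24-day minimum forbids 49 pairs, a 19-day minimum 15 and a 14-day minimum none.
5. *Dose Level -1 (28 days).* The reset window is 26 to 33, so nothing is barred. On a fixed calendar the gap is 28 + b - a, which is below 24 when b - a is -5, -6 or -7. That is 3 + 2 + 1 = 6 of 64 pairs, so the 24-day floor does bind there to a small extent.
6. *DLT period.* On target, doses fall on days 1, 22 and 43, so two lie within the first 42 days. At the 24-day minimum they fall on days 1, 25 and 49, again two. With a minimum of 19 or 14 and the existing -2 allowance, dose 3 can fall 19 + 19 = 38 days after dose 1 (day 39) with resetting, or 40 days after (day 41) on a fixed calendar. Both are inside the period.

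**Part 2: the delay limit**

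1. Twelve weeks is 84 days and 6 weeks is 42 days, a factor of two.
2. The start points also differ. Section 6 counts between doses, Section 6.4 counts from the last dose, and Sections 5.2.3, 5.2.4 and 6.3 speak only of a delay. Forty-two days from the last dose is 42 - 21 = 21 days past due in 21-day cycles, and 42 - 28 = 14 days past due in maintenance. A 6-week delay counted from the due date means a gap of 21 + 42 = 63 days in 21-day cycles; a 12-week delay means 21 + 84 = 105.
3. The cross-reference to Section 6.4 does not reconcile the limits, because Section 6.4 sets 6 weeks itself. Reading 6 weeks as the combination limit and 12 weeks as the limit for all therapy fails against Section 6.3, which stops study therapy at 6 weeks.

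**The case against.** **Ipilimumab can still be given.** With resetting, days 24 to 26 are available and the shift is 3 to 5 days per dose. This stands as a limit on size. A reader might infer that Dose Level 0 cannot be delivered at all; the text does not support that. It bars the on-time dose and, on a fixed calendar, in-window doses 3 and 4.

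**The error does not reveal the intended value.** This stands. The sentence in Cohort 1 with the closest wording points to 19; nivolumab on the same day points to 14. Neither can be called the only correct reading.

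**A shorter minimum has a safety side.** This stands. The 24-day rule keeps dose 3 out of the DLT period, and either replacement lets it in. An unqualified replacement would also loosen the floor at Dose Level -1, a level entered because of DLTs.

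**The delay conflict is narrow.** This largely stands. Section 6.4 excepts steroid tapers and approved non-drug-related holds. It also already stops the combination for most Grade 3 or higher non-skin drug-related events lasting more than 7 days. Other drug-related holds of 6 to 12 weeks remain.

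**A tempting extension fails.** At Dose Level -2 the window is 40 to 47 days, so a reader might infer that in-window doses on days 43 to 47 already break the 6-week limit. Section 6 counts a dose as delayed only when it falls after the 5-day window. An in-window dose is therefore not a delay, nor naturally an interruption under Section 6.4. No exemption is needed.

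**Conclusion.** Both inconsistencies hold, with modest severity.

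The 24-day minimum contradicts the 3-week ipilimumab schedule in two places. It bars day 21 and 4 other window days if dates reset, and makes doses 3 and 4 impossible in window if they do not. The contradiction needs no choice between those readings; only its size depends on the choice, which Section 5.2.4 does not settle.

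The Cohort 2 delay limits differ by a factor of two and use different start points. The practical reach is mainly drug-related holds of 6 to 12 weeks outside the Section 6.4 exceptions.

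A reader might infer that the trial's operating characteristics are damaged. Nothing in the documents supports this: the sample-size, alpha and power statements do not use the dosing interval, and no effect on them or on PFS-6 is claimed.

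**What to change.** 1. In Section 5.2.4 and footnote jj, replace the 24-day minimum with one that permits dosing every 3 weeks, and limit it to every-3-week combination cycles so that the floor at Dose Level -1 is not loosened. The sponsor confirms one of two values:
   - 19 days (18 non-dosing days), on the Cohort 1 pattern, which is the more conservative; or
   - 14 days (13 non-dosing days), which matches nivolumab given the same day. A 19-day minimum would leave two minima for drugs given together.

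   The downside is that either value, with the -2 allowance, lets dose 3 fall inside the 42-day DLT period. The sponsor should accept this knowingly when choosing.

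2. Choose one Cohort 2 delay limit with one start point and state it in Sections 5.2.3, 5.2.4, 6, 6.3 and 6.4. Keep the Section 6.4 exceptions and leave the Cohort 1 limit as it is. Six weeks is the conservative default unless 12 was intended; that is a safety decision for the sponsor.

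The cost is two text edits and the sponsor's confirmation for the first part, and one safety decision with five matching edits for the second. Sample size, power and timelines are unaffected.

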### **5.2.5 Radiation Therapy**

The following applies to patients on cohort 2:

What: On-study Radiation Therapy will be administered according to established, institutional standard-of-care guidelines utilizing one of the following techniques for reirradiation and best clinician judgment:

- fractionated intensity-modulated radiation therapy (IMRT)
- 3-dimensional conformal radiation therapy (3D-CRT)
- or proton beam radiation therapy
- stereotactic radiosurgery
- or fractionated stereotactic radiotherapy

When: To occur prior to initiation of Cycle 1 of Nivolumab + Ipilimumab. Day 1 Cycle 1 of study immunotherapy will be no sooner than 1 week from the completion of XRT, and no later than 12 weeks after completion of XRT.

Where: Participants are permitted to receive re-irradiation on study at the following locations:  
a. the Radiation Oncology Department of the participating institution;  
b. an IRB-approved satellite site of the participating institution;

CONFIDENTIAL

This document is confidential. Do not disclose or use except as authorized.

- c. any NRG Oncology-approved site;
- d. or at another location, with **prior documented approval from the study's Overall PI.**

### 5.3 Study Phases

This study will consist of three phases: screening, treatment and follow-up.

#### Screening Phase:

- Begins by the signing of the informed consent form (ICF) and then establishing the subject's initial eligibility.
- Subject is enrolled.

#### Treatment Phase:

- Participants will begin study therapy within 14 days of completing screening.
- Adverse event assessments will be documented at each visit throughout the study.
- All of the laboratory tests and vital signs will be collected prior to study drug dosing at the time points specified in the Study Calendar (Table 10).
- All of a participant's study scans (screening scan(s), active-treatment scans, and off-treatment scan) will be reviewed for volumetric analysis (*as well as follow-up scans for participants in active follow-up*). See Section 10.2.
- Study drug dosing may be delayed for toxicity. See Section 6.1.
- Treated subjects will be evaluated for response by the investigator according to the iRANO criteria (Section 11.2) every 8 weeks  $\pm$  1 week until disease progression or treatment discontinuation, whichever occurs later.
- Treated subjects will be evaluated for neurologic functioning by the investigator and according to the NANO scale (Section 11.6). Assessments will be performed at baseline scan and every 8 weeks ( $\pm$  1 week) thereafter, at the time of imaging response assessment until disease progression or treatment discontinuation, whichever occurs later.

This phase ends when the subject experiences a confirmed tumor progression, unacceptable toxicity, or other discontinuation criteria, whichever occurs first. For a complete list of reasons for taking a participant off protocol therapy, see Section 5.10.

#### Follow-Up Phase:

Begins when the decision to discontinue a participant from study therapy is made (no further treatment with study therapy).

#### AEs:

- Subjects will be followed for drug-related toxicities until these toxicities resolve, return to baseline or are deemed irreversible. All adverse events will be collected and documented for 30 days after the last dose, and serious adverse events that occur within 100 days after last dose or the start of new anti-cancer treatment, whichever comes first are to be reported per Section 5.10

#### Active Follow-Up:

- Participants who discontinue treatment for reasons other than tumor progression will continue to have tumor assessments at intervals determined by the treating investigator until unequivocal disease progression, initiation of a new therapy, or withdrawal of consent. All radiologically determined disease progression must be confirmed by an additional confirmatory MRI scan up to 12 weeks following the initial assessment of

CONFIDENTIAL

This document is confidential. Do not disclose or use except as authorized.

radiological progression. Investigators may obtain additional follow-up MRI scans prior to 12 weeks as medically appropriate.

Long Term Follow-Up:

- After completion of the first follow-up visits, subjects will be followed every 3 months (+/- 1 month) for survival, post-study-therapy therapies, and future relapses.

#### **5.4 Review of Safety**

Safety of study participants will be monitored on an ongoing basis as described fully in Section 10.1.

#### **5.5 Total Study Duration**

Cohort 1: It is projected that accrual to this cohort will be completed within 24 months after the first participant is enrolled.

Cohort 2: It is projected that accrual to this cohort will be completed within 24 months after the first participant is enrolled.

The final analysis for the primary objective is expected 12 months after the last participant has initiated study therapy. Additional survival follow-up may continue after the primary analysis of survival.

#### **5.6 Treatment Beyond Initial Radiologic Assessment of Disease Progression**

Standard treatment for meningioma (including radiation therapy) may result in a transient increase in tumor enhancement (pseudoprogression) in a subset of participants that eventually subsides without any change in therapy. Pseudoprogression may be difficult to differentiate from true tumor progression and may have important implications for patient management. Accumulating evidence also indicates that some participants treated with immune system stimulating agents may also develop apparent progression of disease (by conventional response criteria) before demonstrating clinical objective responses and/or stable disease.(47) This phenomenon was observed in approximately 10% of subjects in the Phase 1 study of nivolumab and has also been reported for ipilimumab monotherapy.(33) Two hypotheses have been put forth to explain this phenomenon. First, enhanced inflammation within tumors could lead to an increase in tumor size which would appear as enlarged index lesions and as newly visible small non-index lesions. Over time, both the malignant and inflammatory portions of the mass may then decrease leading to overt signs of clinical improvement. Second, in some individuals, the kinetics of tumor growth may initially outpace anti-tumor immune activity. With sufficient time, the anti-tumor activity will dominate and become clinically apparent. Therefore, subjects initially meeting radiologic criteria for disease progression (see Section 6.4) will be allowed to continue study therapy until a second radiologic confirmation of progression performed 12 weeks later as long as the following criteria are met: 1) the participant experiences investigator-assessed clinical benefit; 2) the participant is tolerating the study treatment; and 3) the participant is not experiencing significant neurologic decline that is felt to be attributable to underlying tumor progression.

In order to minimize premature discontinuation of study medication and distinguish pseudoprogression from progressive disease, subjects initially meeting radiologic criteria for disease progression may continue receiving study medication until confirmation of progression with an MRI performed approximately 12 weeks later.

CONFIDENTIAL

This document is confidential. Do not disclose or use except as authorized.

In order to continue study treatment after assessment of initial radiological progression, the following criteria must be met:

- 1) The participant is believed to demonstrate clinical benefit as determined by the investigator;
- 2) The participant is tolerating study medication;
- 3) The participant is not experiencing significant neurologic decline felt to be related to underlying tumor progression.

Participants with confirmed progression (approximately 12 weeks after initially assessed progression) will discontinue study medication and enter the follow up/survival phase of the study. If progression is confirmed then the date of disease progression will be the first date the participant met the criteria for progression.

In those cases in which radiologic progression cannot be differentiated from pseudoprogression and it is the investigator's opinion that a surgical resection to obtain tumor tissue for histopathology is in the participant's best interests, a surgical resection may be performed. Tumor biopsy samples (blocks or slides) must be submitted for review by a local neuropathologist for histopathologic assessment of progression versus treatment-related changes. If tumor pathology confirms progression, then the participant will be discontinued from study medication per protocol discontinuation criteria and the date of progression will be the day that it was first suspected. If tumor pathology reveals treatment-related changes and does not confirm disease progression, the participant may continue study medication. An MRI after the resection is required prior to treatment continuation. The participant will then continue all on-treatment tumor assessments as per the treatment schedule.

In addition, patients who develop progressive disease at an anatomical site that did not receive study radiation therapy, either as progression of existing lesion(s) or as a new site of disease, may be allowed to continue study therapy as long as site(s) of disease that received study radiation therapy are at least stable. Study radiation therapy will be administered to such sites of progressive disease utilizing a type and schedule of radiation therapy deemed to be best suited for the patient based on assessment by the treating investigator. The date of study therapy progression will correspond to the date of initial progressive disease, but the ability of study therapy including radiation therapy with immune checkpoint blockade to control such sites of tumor progression will be assessed.

